11. SAFETY ANALYSIS

The purpose of this section is to define the safety analysis for the study. All summaries of safety data will be conducted using the safety population. Descriptive statistics will be provided by disease cohort and treatment arm.

11.1. Adverse Events

Adverse events will be coded using Medical Dictionary for Regulatory Activities (MedDRA) of Version 22. Adverse event listings will include the verbatim term and the MedDRA preferred term. The intensity of AEs will be graded according to the Common Terminology Criteria for Adverse Events (CTCAE) Version 4.03 or higher. For any AE not listed in the CTCAE grading system, the intensity of these events will be assessed by the Investigator using a 5-point scale as described in protocol.

If a subject experiences multiple AEs under the same PT (SOC), the subject will be counted only once for that PT (SOC). If a subject experiences the same AE more than once with a different intensity grade, the event with the highest grade will be tabulated in “by grade” tables. In addition, AEs with a missing intensity will be presented in the summary table as an intensity category of “Missing” and will not be imputed.

Treatment emergent adverse events (TEAEs) are defined as AEs occurring or worsening on or after the date of the first dose of the study treatment (CC-486 or durvalumab) and within 28 days after last dose of CC-486 or 90 days after last dose of durvalumab. A treatment-related TEAE is defined as a TEAE where the causal relationship was assessed by the investigator as “Suspected”. If the relationship between a TEAE and a study drug is missing, the TEAE will be considered to be related to the study treatment.

Summary tables for the incidence of TEAEs will be summarized by disease cohort, treatment arm, SOC, and PT within SOC. They will be sorted by alphabetically order of SOC and PT, and then sorted by decreasing frequencies, unless otherwise specified. Following tables will be generated:

- TEAEs;
- TEAEs related to CC-486 only, durvalumab only, or CC-486 or durvalumab;
- TEAEs of CTCAE grade 3 or 4;
- TEAEs related to CC-486 only, durvalumab only, or CC-486 or durvalumab with CTCAE grade 3 or 4;
- TEAEs with death outcome;
- TEAEs with death outcome related to CC-486 only, durvalumab only, or CC-486 or durvalumab;

- Serious TEAEs;
- Serious TEAEs related to CC-486 only, durvalumab only, or CC-486 or durvalumab;
- TEAEs leading to discontinuation of CC-486 only, durvalumab only, or CC-486 or durvalumab;
- TEAEs leading to dose reduction of CC-486;
- TEAEs leading to dose interruption of CC-486 only, durvalumab only, or CC-486 or durvalumab;
- TEAEs leading to infusion interruption of durvalumab.

As well as

- TEAEs by cycle of onset as well as the safety run-in period;
- TEAEs related to CC-486 only, durvalumab only, or CC-486 or durvalumab, by cycle of onset;
- TEAEs by maximum CTCAE grade;
- TEAEs related to CC-486 only, durvalumab only, or CC-486 or durvalumab, by maximum CTCAE grade;
- Common ($\geq 10\%$) TEAEs;
- Common ($\geq 10\%$) TEAEs related to CC-486 only, durvalumab only, or CC-486 or durvalumab;
- By age category: <65 , $65-74$, ≥ 75 ;
- By gender.

All deaths, on treatment deaths, off treatment deaths and causes of death will be summarized from the Death form in the CRF. Deaths within or 28 days after last dose of CC-486 or 90 days after the last dose of durvalumab will be summarized separately.

Individual subject listing of AEs will be presented. In addition, the following listings will be provided:

- Listing of SAE;
- Listing of TEAEs leading to permanent withdrawal of any study drug
- Listing of all TEAEs with outcome of death
- Listing of all subjects who died

CCI [REDACTED]

The AEs CCI [REDACTED]

[REDACTED] The following TEAEs CCI [REDACTED]

- Myelosuppression (neutropenia, thrombocytopenia, anemia, general myelosuppression)
- Gastrointestinal disorders
- Hemorrhagic events
- Infections
- Renal failure
- Hepatic failure
- Ischemic colitis
- Interstitial lung disease
- Cardiac events (cardiac failure, cardiac arrhythmias, myocardial infarction)
- Anxiety, Confusional state, Insomnia
- Other psychiatric disorders
- Tumour lysis syndrome

Although not determined as an important risk in the Vidaza RMP, gastrointestinal events as defined by System Organ Class Gastrointestinal disorders will also be summarized as an adverse event of special interest for this study.

For durvalumab, following are the AESIs for Ongoing Surveillance Activities based on pre-defined search criteria as provided by AstraZeneca/MedImmune:

- Diarrhoea
- Colitis
- Intestinal perforations
- Pneumonitis
- Hepatitis
- Hepatic laboratory parameters reported as AEs
- Adrenal insufficiency
- Type 1 diabetes mellitus
- Hypophysitis
- Thyroiditis

- Hyperthyroidism
- Thyroid laboratory parameters reported as AEs (increased thyroid activity))
- Hypothyroidism
- Thyroid laboratory parameters reported as AEs (decreased thyroid activity))
- Rash
- Dermatitis
- Nephritis
- Renal laboratory investigations reported as AEs
- Pancreatitis
- Pancreatic laboratory investigations reported as AEs
- Myocarditis
- Myositis
- Myasthenia gravis
- Guillain-Barré syndrome
- Other rare/miscellaneous
- Hypersensitivity / Anaphylactic reactions
- Infusion related reaction

After review of the data, there may be other AEs of special interest identified. For summaries based on selected MedDRA preferred terms, the final selection of inclusive preferred terms will be performed based on review of final data to ensure all relevant terms are captured. Summary table will be provided for all TEAEs included in the above-mentioned AEs of special interest.

- All TEAEs
- TEAEs of Grade 3 or 4
- Serious TEAEs
- TEAEs leading to study drug withdrawal
- TEAEs leading to study drug dose reduction
- TEAEs leading to study drug dose interruption
- TEAEs leading to death

The incidence rate per 100 person-years will also be derived for each AESI.

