1.4.1. Azacitidine Exposure

While injectable hypomethylating agents (azacitidine for injection and decitabine) remain the standard of care in the treatment of IPSS higher-risk MDS, as many as half of affected patients do not respond to treatment, and nearly all those who do respond will eventually relapse. Upon failure of treatment with azacitidine for injection and/or decitabine, the prognosis for patients

with higher-risk disease is dismal, with median overall survival on the order of 4-6 months (Prebet, 2011; Jabbour, 2010). Similarly, injectable HMAs are approved for treatment of IPSS lower-risk MDS in some countries, and while there are few data to characterize outcomes in lower-risk disease following failure of these agents, prognosis is poor and for patients who are not eligible for allogeneic stem cell transplant, no proven treatment options currently exist (Jabbour, 2013).

Aberrant hypermethylation of DNA is a feature of myelodysplastic syndromes, and is implicated in the pathogenesis and progression of disease (Gore, 2006). This supports the notion that epigenetic changes play an important role in MDS transformation and may be exploited. However, association between the degree of constitutive methylation and magnitude of reduction in methylation state via treatment with HMAs has not been clearly correlated with treatment outcomes (Follo, 2009).

Azacitidine is a cytidine analog that may, in part, exert its antineoplastic effect by incorporation into DNA of cycling cells and subsequent hypomethylation through inhibition of DNA methyltransferases. Optimal drug activity may require an increased window of exposure to malignant cells to increase the opportunity for cycling cells to incorporate drug (Mahfouz, 2013; Stresemann, 2008).

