4.2. Study Design Rationale

This is a Phase 2, international, multicenter, randomized, parallel group, open-label study designed to evaluate the efficacy and safety of treatment with CC-486 (an orally-available cytidine analog) alone and in combination with durvalumab (a monoclonal antibody targeting the Programmed Cell Death Ligand 1 [PD-L1]) in subjects with myelodysplastic syndromes when an objective response is not achieved through treatment with an injectable hypomethylating agent (iHMA). The randomized study design reduces bias in subject selection by treatment group, and enables a valid comparison of efficacy and safety between treatment groups. This will allow for selection of the appropriate treatment group for further evaluation in the post-iHMA setting.

The study population represents the group of patients with MDS that have exhausted available HMA treatment options. No additional medical intervention is currently approved in this setting and prognosis for members of this population is dismal.

The study will evaluate the two treatment regimens in two subsets of subjects who fail to respond to iHMA treatment: those with *stable disease* (with no hematologic response or improvement) associated with the iHMA, and those with *disease progression* during or following iHMA treatment. The study excludes subjects who respond to injectable therapy but subsequently relapse, because this group is thought to represent an especially **hard-to-treat** segment of the population where additional disease control is generally unlikely with this, or other, experimental agents. The SD and PD sub-populations will be analyzed separately for the monotherapy and combination therapy treatment arms.

A safety run-in phase of the study will explore the safety and tolerability of CC-486 alone and in combination with durvalumab to confirm that there are no overlapping or synergistic toxicities limiting the ability of the two drugs to be delivered in combination, and to determine the initial dose and schedule to be applied for the randomized portion of the study. Once a recommended dose and schedule for the combination has been identified as described in Section 4.1.2, enrollment into the randomized treatment phase may begin.

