All AEs will be recorded by the investigator from the time the subject signs informed consent until 28 days after the last dose of CC-486, 90 days after the last dose of durvalumab, or until the Treatment Discontinuation Visit, whichever is later and those SAEs made known to the investigator at any time thereafter that are suspected of being related to IP. Adverse events and SAEs will be recorded on the AE page of the CRF and in the subject's source documents. All SAEs must be reported to Celgene Drug Safety within 24 hours of the investigator's knowledge of the event by facsimile, or other appropriate method, using the SAE Report Form, or approved equivalent form.

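### Unequal post-treatment windows (28 against 90 days) are expected to push crude by-arm TEAE and windowed-death incidence up in the combination column even at equal risk, and no common-window table is planned

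*SAP*

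**What the plan says.** SAP 11.1 defines a TEAE as an event that starts or worsens on or after the first dose and "within 28 days after last dose of CC-486 or 90 days after last dose of durvalumab". A subject is counted once per preferred term or system organ class, so the tables are crude subject incidence. SAP 11 sets the layout: "Descriptive statistics will be provided by disease cohort and treatment arm".

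For deaths there are two layers. First, "All deaths, on treatment deaths, off treatment deaths and causes of death will be summarized from the Death form in the CRF". Then, in addition, "Deaths within or 28 days after last dose of CC-486 or 90 days after the last dose of durvalumab will be summarized separately".

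Time at risk enters only for adverse events of special interest (AESIs): "The incidence rate per 100 person-years will also be derived for each AESI". The person-time is not defined, and no such rate is planned for the other TEAE tables. TEAEs are also tabulated by cycle of onset.

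The windows follow the protocol's data collection. Under Protocol 11.1, adverse events are recorded "until 28 days after the last dose of CC-486, 90 days after the last dose of durvalumab, or until the Treatment Discontinuation Visit", whichever is latest. Protocol 4.2 says that randomization "enables a valid comparison of efficacy and safety between treatment groups".

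**The concern.** In a crude incidence table, the arm observed for longer collects more events. Here the length of observation after stopping depends on the arm, and the extra days fall in a period that is unlikely to be quiet. These subjects have failed injectable hypomethylating therapy, for which Protocol 1.4.1 cites, in higher-risk disease, "median overall survival on the order of 4-6 months".

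AML progression gives a concrete case. Protocol 6.7.2 and 11.7.1 have it reported as a serious event regardless of cause, in both arms, until death or study closure. Take an AML event 60 days after the last CC-486 dose in a subject who completed the last cycle. In the combination arm that is 80 days after the last durvalumab infusion, so it is a serious TEAE. The same event in a monotherapy subject is reported but is not a TEAE.

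At stake is how a reader judges the added toxicity of durvalumab from columns placed side by side. Part of any excess in all, serious, Grade 3-4 or fatal TEAEs, or in windowed deaths, would come from the longer count.

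**Working it through.** The documents give no calculation for these windows, so there is no stated figure to reproduce.

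**Inputs from the documents.** Windows of 28 and 90 days (SAP 11.1). Durvalumab on Day 1 and CC-486 on Days 1-21 of a 28-day cycle (Protocol 4.2, 8.2.2.1). Median survival of 4-6 months (Protocol 1.4.1). Month = 30.4167 days (SAP 5.1.1). 65 subjects enrolled (Protocol 4.1); 13 in the monotherapy run-in and two fully enrolled monotherapy Stage 1 cohorts (Amendment 4 justification); 16 per Stage 1 cohort (SAP 4.3). I read the combination window as ending at the later of the two limits.

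**Step 1: net extra tail.**
- Last cycle completed: the durvalumab limit is Day 1 + 90 = 91 and the CC-486 limit is Day 21 + 28 = 49. The gap is 91 - 49 = 42 days. Counted from the last CC-486 dose, the windows are 91 - 21 = 70 days against 28.
- CC-486 on the 14-day schedule: 91 - (14 + 28) = 49 days.
- Both drugs last given together: 90 - 28 = 62 days.
- Durvalumab stopped 62 or more days before the last CC-486 dose: at most 90 - 62 = 28 days remain, so the gap is nil.

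**Step 2: post-dose deaths in the window, with the same hazard in both arms.** Assumption: constant hazard from the last CC-486 dose with median m months, so P(d) = 1 - exp(-ln 2 × d / (30.4167 m)).

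| Median | 28 days | 70 days | 90 days | 70 vs 28 | 90 vs 28 |
|---|---|---|---|---|---|
| 4 months | 14.7% | 32.9% | 40.1% | 2.2 | 2.7 |
| 6 months | 10.1% | 23.4% | 29.0% | 2.3 | 2.9 |

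**Step 3: TEAE incidence, with the same hazard in both arms.** Event probability q per 28 days is assumed, not documented, and is held constant on and off treatment. With c completed cycles, the time from first to last CC-486 dose is L = 28c - 8 days, and P(t) = 1 - (1 - q)^(t/28). Compare t = L + 28 (monotherapy) with t = L + 70 (combination, 42-day gap).

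Example with c = 2 and q = 10%: L = 48, P(76) = 24.9%, P(118) = 35.9%, ratio 1.44.

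| q per 28 days | 2 cycles | Ratio | 6 cycles | Ratio |
|---|---|---|---|---|
| 2% | 5.3% → 8.2% | 1.53 | 12.7% → 15.3% | 1.21 |
| 5% | 13.0% → 19.4% | 1.50 | 29.1% → 34.4% | 1.18 |
| 10% | 24.9% → 35.9% | 1.44 | 50.7% → 57.9% | 1.14 |
| 20% | 45.4% → 61.0% | 1.34 | 77.6% → 84.0% | 1.08 |

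For the 62-day gap, the same grid gives ratios of 1.11 to 1.78. Events accrued on treatment dilute the tail, so these ratios are smaller than those for post-dose deaths.

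**Step 4: number of subjects.** Combination subjects: at most about 65 - 13 - (2 × 16) = 20, if no monotherapy subject was replaced. With 20 subjects, the 42-day gap adds about 20 × (0.234 - 0.101) = 2.7 to 20 × (0.329 - 0.147) = 3.6 in-window deaths under Step 2.

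**Step 5: common window.** With one limit for both arms, equal hazards and equal time on treatment, the two probabilities coincide and the spurious difference is zero.

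**The case against.** The strongest reply is that the comparison hardly exists. SAP 4.1 starts 1:1 randomization only when both run-ins are finished. The Amendment 4 justification says that the combination run-in cohort was stopped on 16 January 2018, and SAP 13 says that no optimal dose could be determined. On these texts no combination subject was randomized, so a reader might infer a biased randomized comparison that did not take place. A small dose-finding group would stand beside monotherapy subjects from a run-in and two later cohorts, in tables that are only descriptive. A common window does not make that a valid estimate of the effect of durvalumab. This stands, and it limits the weight of the point.

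A reader might also infer that all deaths are counted unequally. They are not: all deaths are summarized without a window, subjects who died are listed, and overall survival is by Kaplan-Meier (SAP 10.2.1). Nor is every safety table affected. The by-cycle tables use a last-cycle end defined alike in both arms (SAP 5.1.2). Dose-modification tables mainly reflect time on treatment. AESI rates may partly offset the bias if person-time covers the tail, and time to AML has its own Kaplan-Meier analysis (SAP 10.2.6).

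The windows also match the protocol's collection rule, and a 90-day follow-up after durvalumab is not itself at fault.

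What does not stand is that the stop makes the point moot. The safety population takes in all treated subjects with a post-dose safety assessment (SAP 5.2.3), so run-in combination subjects are included. The SAP was amended in June 2019 and March 2020, after the stop. The PK outputs were dropped, but the by-arm TEAE tables remain. Safety alone and in combination is a secondary objective (SAP 3.2).

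**Conclusion.** The point holds within limits. At equal hazards, the crude by-arm tables of all, serious, Grade 3-4 and fatal TEAEs, and the windowed-death table, are expected to run higher in the combination column, and no planned common-window table corrects this.

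The extra tail is usually about 42 days. For TEAE incidence that means roughly 1.1 to 1.5 times, under assumed constant hazards and 2 to 6 cycles. If drug-related events subside after stopping, the inflation is smaller. For post-dose deaths in the window it means 10-15% against 23-33%. That range is illustrative: the 4-6 month median is cited for higher-risk disease after treatment failure, Protocol 7.1 also admits lower-risk disease, and the figure is applied here from the last study dose.

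Two stronger readings are not supported. The roughly twofold ratio for deaths does not carry over to the TEAE tables. And it cannot be said that the tables will show excess harm: with about 20 subjects or fewer, chance and the lack of randomization may outweigh the window. This is an avoidable bias that is cheap to remove, in tables of modest weight.

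**What to change.** In SAP 11.1, keep the 28/90-day tables. For the main TEAE, serious, Grade 3-4 and fatal TEAE tables and the windowed-death table, wherever both arms appear, add a version with one window: first dose to 28 days after the last dose of CC-486, or after the last dose of any investigational product if durvalumab was continued alone. Show later combination-arm events, up to 90 days after durvalumab, in a separate table so that late immune-mediated events stay visible.

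A common 90-day window is not available for adverse events, because routine monotherapy collection ends 28 days after CC-486 or at the discontinuation visit if later. The common window does not adjust for different time on treatment or for the absence of randomization, and a footnote should say so.

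The cost is a paragraph of SAP text and a repeat run of existing tables with a second date cut. No new data are needed. The downside is a few more tables.

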10.7. Safety Analysis

The safety population will be used for all safety evaluations.

Adverse events will be coded using Medical Dictionary for Regulatory Activities (MedDRA). Adverse event listings will include the verbatim term and the MedDRA preferred term. Adverse events will be summarized by worst severity grade. Adverse events, as well as treatment-emergent AEs, will be summarized by system organ class, and preferred term. Adverse events leading to death or to discontinuation from treatment, events classified as NCI CTCAE (Version 4.03) Grade 3 or Grade 4, adverse events related to IP, serious adverse events and Adverse Events of Special Interest (AESI) will be summarized separately.

Clinical laboratory results will be summarized descriptively and will include a display of change from baseline. Laboratory values outside of the normal ranges will be identified. Clinically significant hematologic and non-hematologic laboratory abnormalities that meet Grade 3 or Grade 4 criteria according to the CTCAE will be listed and summarized.

Vital sign measurements will be listed for each subject at each visit. Descriptive statistics for vital signs, both observed values and changes from baseline, will be summarized.

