11.5. Reporting of Serious Adverse Events

Any AE that meets any criterion for an SAE requires the completion of an SAE Report Form in addition to being recorded on the AE page/screen of the CRF. All SAEs must be reported to Celgene Drug Safety within 24 hours of the investigator's knowledge of the event by facsimile, or other appropriate method, using the SAE Report Form, or approved equivalent form. This instruction pertains to initial SAE reports as well as any follow-up reports.

The investigator is required to ensure that the data on these forms is accurate and consistent. This requirement applies to all SAEs (regardless of relationship to IP) that occur during the study from the time the subject signs informed consent until 28 days after the last dose of CC-486, 90 days after the last dose of durvalumab, or until the Treatment Discontinuation Visit, whichever is later, and any SAE made known to the investigator at any time thereafter that are suspected of being related to IP. SAEs occurring prior to treatment (after signing the ICF) will be collected.

The SAE report should provide a detailed description of the SAE and include a concise summary of hospital records and other relevant documents. If a subject died and an autopsy has been performed, copies of the autopsy report and death certificate are to be sent to Celgene Drug Safety as soon as these become available. Any follow-up data should be detailed in a subsequent SAE Report Form, or approved equivalent form, and sent to Celgene Drug Safety.

Where required by local legislation, the investigator is responsible for informing the IRB/EC of the SAE and providing them with all relevant initial and follow-up information about the event.

The investigator must keep copies of all SAE information on file including correspondence with Celgene and the Institutional Review Board (IRB)/Ethics Committee (EC).

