The total number of subjects for the randomized treatment phase will range from approximately 64 (at Stage 1) to 164 (Stage 1 plus Stage 2) for the four subject cohorts. More subjects can potentially be recruited for replacement of non-evaluable subjects, if needed. Details can be found in the Sample Size section.

PK Sampling:

Blood samples for pharmacokinetic analysis will be collected from approximately 10-12 evaluable subjects received the combination treatment arm at selected sites. This will enable assessment of drug-drug interactions.

Follow-up Phase

All subjects who receive at least one dose of CC-486 (durvalumab) in the safety run-in or randomized treatment phase and discontinue treatment for any reason will be followed for at least 28(90) days after their last dose of CC-486 (durvalumab) for the assessment of safety-related parameters. After the 28(90)-day period for CC-486 (durvalumab), only SAEs made known to the investigator that are suspected of being related to treatment with CC-486 (durvalumab) need to be reported.

A 28(90)-day follow-up visit will be conducted 28(90) (± 3) days following the last dose of CC-486 (durvalumab) or during the final treatment phase study visit (whichever date is later) for assessment of the safety-related parameters.

Subjects in follow-up will then be contacted every 3 months from the date of the 28(90)-day follow up visit for CC-486 (durvalumab) until death, loss-to follow-up, withdrawal of consent to further follow-up, or study closure to collect information related to survival, subsequent MDS-related therapies, and disease progression to AML. This will continue until the last active subject completes approximately 12 months of treatment and/or follow-up unless additional follow-up is needed to evaluate time-to-event endpoints. Follow-up contacts will routinely be conducted by telephone unless special circumstances exist.

Study Closure

The study is expected to close when the last subject completes approximately 12 months of treatment and/or follow-up, unless additional follow-up is needed to analyze time-to-event endpoints.

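### Protocol 10.7 promises summaries of all AEs and SAEs, but every visible incidence table in SAP 11.1 is limited to TEAEs, so late non-fatal drug-suspected SAEs reach no visible related or serious AE table

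*SAP*

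**What the plan says.** Protocol 10.7 (Safety Analysis) names two kinds of event side by side: "Adverse events, as well as treatment-emergent AEs, will be summarized by system organ class, and preferred term". It then promises separate summaries of AEs leading to death or discontinuation and of Grade 3 or 4 events, and adds that "adverse events related to IP, serious adverse events and Adverse Events of Special Interest (AESI) will be summarized separately". None of these is restricted to TEAEs.

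On collection, Protocol 11.1 records all AEs from consent until 28 days after CC-486, 90 days after durvalumab, "or until the Treatment Discontinuation Visit, whichever is later and those SAEs made known to the investigator at any time thereafter", provided the late SAEs are suspected to be IP-related. Protocol 11.5 repeats this for "any SAE made known to the investigator at any time thereafter that are suspected of being related to IP". SAP 4.1 agrees: after the 28- or 90-day period, "only SAEs made known to the investigator that are suspected of being related to treatment with CC-486 (durvalumab) need to be reported".

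SAP 11.1 defines a TEAE as an AE occurring or worsening from first dose and "within 28 days after last dose of CC-486 or 90 days after last dose of durvalumab". It defines treatment-related only for events that are already TEAEs. It introduces its outputs thus: "Summary tables for the incidence of TEAEs will be summarized by disease cohort, treatment arm, SOC, and PT within SOC". The listings of all AEs and of SAEs carry no TEAE limit; the listing of events leading to permanent withdrawal does. Deaths on and off treatment, with causes, are summarised from the Death form. The SAP amendment log has two entries, on PK outputs and AESI search paths.

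**The concern.** Because the protocol distinguishes AEs from TEAEs in a single sentence, AE there cannot be shorthand for TEAE. The SAP delivers only the TEAE half and does not say that it is departing from the protocol.

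The events affected are not random leftovers. Apart from AML progression, SAEs that the investigator attributes to the drug are the only AEs the protocol still asks for once the collection period has closed, and it asks for them because of suspected causality. If the SAP is followed as written, someone reading the related and serious AE tables would see none of them and would have no sign that they exist. A listing puts them on record, but it does not meet a promise to summarise.

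**Working it through.** No sample size, power or alpha is involved, so the check sets the texts side by side.

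**1. Which tables does SAP 11.1 show?** The first list has 12 items, the second has 8 (six named TEAE tables plus the age and gender cuts), and the AESI list has 7: 12 + 8 + 7 = 27. Of these, 25 name TEAEs, and the two subgroup cuts sit under the TEAE introduction. None covers all AEs, all SAEs or all related AEs. The AESI tables are counted for completeness only; part of the surrounding text is redacted and nothing is claimed about them.

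**2. Where does each kind of event go?**

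| Event | Collected? | Visible related or serious AE table | Elsewhere |
|---|---|---|---|
| Suspected SAE, onset inside the window | Yes | Yes | Listings |
| Suspected SAE, onset after the window, non-fatal | Yes (Protocol 11.1, 11.5; SAP 4.1) | None | AE and SAE listings |
| Suspected SAE, onset after the window, fatal | Yes | None | AE and SAE listings; death summary |
| AML progression, any time | Yes, as an SAE (Protocol 11.7.1) | Only if inside the window | Time-to-event analysis (SAP 10.2.6) |

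The second row is the main gap. It follows from the definitions: an event with onset after the window is not a TEAE, so it cannot be a treatment-related TEAE or a serious TEAE.

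**3. Secondary gap: prolonged monotherapy hold.** Collection runs to the later of 28/90 days or the Treatment Discontinuation Visit; the TEAE window has no such clause. Inputs: 28-day cycles, so the next cycle is due on Day 29; delays of up to 42 days are permitted (Protocol 4.1.3); treatment should stop if the delay exceeds 56 days, unless there is clinical benefit (Protocol 8.2.5). Assume that all planned doses were taken, CC-486 never restarts, and the visit falls on Day 29 + d, where d is the delay in days.

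- 21/28 schedule: last dose Day 21, window ends Day 21 + 28 = 49. Uncovered days before the visit = (29 + d) − 49 − 1 = d − 21. At d = 42 this is 21 days; at d = 56 it is 35.
- 14/28 schedule: last dose Day 14, window ends Day 42. Uncovered days = d − 14, giving 28 and 42.
- If CC-486 restarts, the last dose moves later and the gap closes.
- Combination arm with both drugs held: durvalumab is given on Day 1, and a 56-day delay puts the visit on Day 85, which is 84 days after the infusion and inside the 90-day window. No gap.

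An AE that starts in the uncovered days and is recorded as the cause of stopping misses both the discontinuation table and the TEAE-limited withdrawal listing. It stays in the general AE listing with its preferred term.

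**The case against.** The strongest reply is that TEAE tables are normal practice, that Protocol Section 10 describes itself as an overview, and that no event disappears: the AE and SAE listings are not TEAE-limited, deaths are summarised regardless of timing, and with 65 subjects enrolled a reader can find a few late SAEs by eye. Late SAEs are also passively reported, so they do not belong in incidence rates. Most of this stands, and it limits the severity. It does not explain why the SAP drops a summary the protocol names, and it argues for a separate counts table rather than for none.

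The hold scenario is narrow, as an opponent would say. An AE that began during dosing and caused the hold is already a TEAE. The gap needs a new late-onset event recorded as the reason for stopping.

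A reader might draw stronger inferences that the documents do not support:

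- *The 28/90-day window is wrong.* It matches the protocol's safety follow-up periods.
- *A late AE that ends monotherapy would show only as a reason in the disposition table.* The general AE listing would carry it, with verbatim and preferred terms.
- *No table anywhere covers these events.* Parts of SAP 11.1 are redacted, so only the visible outputs can be judged.
- *AML progression is left unanalysed.* SAP 10.2.6 covers it.

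**Conclusion.** The mismatch is real and should be corrected. Every visible AE incidence table in SAP 11.1 is limited to TEAEs, against an explicit protocol statement and without a stated reason. By definition, every non-fatal suspected SAE with onset after the window falls outside the visible related and serious AE tables. The documents do not give the number of such events, and it may be zero. The hold gap is minor and conditional on the assumptions set out above.

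The primary endpoint and the Stage 1 decision are unaffected. The conclusion assumes that the redacted text does not contain the missing summaries and that the protocol's distinction between AEs and TEAEs was intended.

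**What to change.** In SAP 11.1:

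1. Add the all-AE and all-SAE summaries by SOC and PT that Protocol 10.7 calls for, by cohort, with events after the TEAE window shown separately.
2. Add a counts-only table of SAEs assessed as Suspected with onset after the window. Keep it out of TEAE incidence and person-year rates, because capture at that stage is passive.
3. Remove the TEAE limit from the table of AEs leading to discontinuation and from the permanent-withdrawal listing.

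The TEAE definition can stay, and the TEAE flag need not be re-run. All the data are already collected. The cost is two or three extra tables, one changed listing and slightly less favourable AE counts.
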